#### **4. Study Procedures**

- a. Study design, including the sequence and timing of study procedures (distinguish research procedures from those that are part of routine care).

Study Design: After the decision to proceed with shoulder replacement surgery, patients will be asked to participate in this prospective randomized clinical trial.

Study Groups:

- Group 1 will receive interscalene nerve block.
- Group 2 will receive liposomal bupivacaine with local bupivacaine for postoperative analgesia.

Study Procedures:

1. Before Surgery: The Informed Consent process will be completed prior to any data collection. Consent will be completed after explanation of each treatment group and the data to be collected. The following baseline data will be collection prior to surgery:

- Demographics (including age, sex, BMI, work status, living environment)
- Medical and Surgical History
- ASA Physical Status Classification
- Charlson Comorbidity Index Score
- Pain History and Medications
- VAS pain score

2. Randomization: Subjects will be randomized prior to surgery into one of the two perioperative analgesia groups. Randomization will be stratified by gender.

3. Surgery/Inpatient Stay:

- Group 1: Patients in the interscalene nerve block group will be given a single shot block in the preoperative area by a fellowship-trained anesthesiologist. The shot will contain a local anesthetic like 5% Ropivacaine (5 mg/1 mL) with a 44 millimeter 22 gauge needle with the patient in the supine position.
- Group 2: The surgeon at each site will be trained prior to enrollment on the correct way to perform Exparel injections intraoperatively. The surgeon will give patients in the liposomal bupivacaine group the periarticular injection

containing 266 mg of the drug in 40 mL injectable saline in the operating room; local 0.5% bupivacaine-epinephrine will also be used not to exceed dose limits.

- Surgical/Inpatient Data Collection:
  - Pre-op procedure time
  - Surgical time
  - PACU time
  - Admission/Discharge time and date
  - Estimated blood loss
  - Procedures performed
  - Inpatient pain medications administered
  - Patient VAS scores every 6 hours after surgery

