#### 4. After Discharge:

- Patients will record the following information after discharge up until 96 hours from their surgery:
  - VAS scores every 6 hours
  - Pain medication consumption (dosages, times)
  - Opioid-related side effects
  - Level of satisfaction with pain management
- Study staff may conduct reminder phone calls to ensure patients complete outpatient data collection. The outcome assessor will be blinded to the treatment group.
- Patients will record their VAS pain scores again at their 1st postop appointment, which typically occurs 10-18 days after surgery.

Sample Size: There will be 60 patients in each group, for a total study population of n = 120.

Study Locations: This will be a multi-center study. The sample size will enroll 120 (to account for 15% drop out rate) patients total, with approximately 30 patients enrolled at each site. The other participating sites are as follows:

[name]  
Sports Medicine and Shoulder Service  
University of Texas, Southwestern Medical Center  
[name]  
[name]

[name]  
MedStar St. Mary's Hospital  
[name]  
[name]

[name]  
William Beaumont Army Medical Center  
[name]  
[name]

**Aim #2:** Determine the length of stay of liposomal bupivacaine compared to interscalene nerve block in patients undergoing total shoulder arthroplasty and calculate costs associated with any differentials.

- b. Study duration and number of study visits required of research participants.

Patients will be enrolled in this study for 2 weeks after their surgical date. This time frame will include their hospital stay and include their time at home after discharge up until 96 hours after their surgery, and their 2-week postop appointment data. If patients are not scheduled for their postop appointment within 10-18 days after surgery (which is standard clinical practice), the study team will call the patient to obtain their pain score and medication data. Patient names will be stored in a password-protected database for 30 days after discharge to calculate 30-day readmission rates.

Routine patient follow up is typically at 3, 6, and 12 months for the first year. Pain data and patient reported outcomes are collected at these visits as routine clinical care. Patients routinely complete the ASES and EQ-5D questionnaires at their 12 month follow up appointment.

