## 7. Study Statistics

- a. Primary outcome variable.

- VAS pain score at 24 hours postop.

- b. Secondary outcome variables.

- VAS scores at all other data points,

- Pain medication consumption (narcotics, NSAIDs, Tylenol)
- Opioid-induced side effects (nausea, vomiting, constipation)
- Length of hospital stay
- 30 day readmission rate.

- c. Statistical plan including sample size justification and interim data analysis.

A power analysis was performed to determine the sample size needed to determine noninferiority between groups with respect to VAS pain score. The minimal clinically important difference of VAS is 1.4 cm^13. The number was found to be 42 patients in each group, for a total n = 84. To ensure we reach this number, each of the 4 sites will aim to enroll 30 patients, to account for drop out.

The age of the two treatment groups will be compared using t-test. Sex distribution and the ASA scores of the groups will be compared using a chi-squared test and a Fisher exact test, respectively.

The median and interquartile range of the VAS scores at each of the time points measured will be tabulated by treatment group, and at each time point the difference between groups will be tested using non-parametric rank sum tests.

We will test the longitudinal trajectory of VAS scores over time, taking into account repeated measurements in the same patients using linear mixed model analysis. Treatment group, time period as a categorical variable, and the interaction between treatment and time period will be included as fixed effects, and patient ID will be included as the random effect. An initial omnibus test will be performed for all treatment and treatment by time interaction effects. If significant, the treatment by time interaction will be tested subsequently for each of the measurement periods.

The association of day of discharge (as a categorical variable) with treatment will be tested using the Fisher exact test.

- d. Early stopping rules.

We will monitor operative and post-operative complications including implant failures, nerve injuries, hematomas, and infections. We do not anticipate issues with these complications, as both techniques are in routine use in our current clinical practice. We did not find any differences in the complication rates in our retrospective cohort analysis.

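### Site is in neither the randomisation strata nor any planned analysis of a four-site trial; this costs some precision and leaves chance site imbalance uncorrected, but causes no bias

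*Combined protocol and SAP*

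**What the plan says.** Section 4 (Study Procedures) states "Randomization will be stratified by gender". It does not give a block size, or say whether there is one list for the trial or a list at each site. Under Study Locations, recruitment is spread over four sites, "with approximately 30 patients enrolled at each site". Section 5 names one surgeon for each.

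Several features of care may differ by site. For the nerve block group, section 4 says "The shot will contain a local anesthetic like" and then gives an example, so the agent is not fixed. Inpatient analgesics are recorded, but no common regimen is described. For the infiltration group, section 4 says "The surgeon at each site will be trained prior to enrollment on the correct way to perform Exparel injections intraoperatively".

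Section 7c plans a rank-sum test at each time point (which covers the 24-hour primary outcome), a linear mixed model and a Fisher exact test for day of discharge. The fixed effects of the mixed model are treatment, time period and their interaction, and "patient ID will be included as the random effect". None of these analyses contains site, or gender, which is the stratification factor itself.

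**The concern.** Operator, block agent, background analgesia and discharge habits plausibly travel together within a site, so site may well predict 24-hour VAS, opioid use and length of stay. The pilot data in section 3 come from a single surgeon and say nothing about how much sites differ.

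Two things are at stake. First, nothing in the plan keeps the arms balanced within site or corrects for an imbalance, so the one realised estimate can be moved by which sites happened to contribute more patients to an arm. Second, whatever variance lies between sites is left in the error term of every comparison. In addition, no output in the plan would show whether the result rests on one site.

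**Working it through.** **Inputs from the documents.** Four sites of about 30. "There will be 60 patients in each group, for a total study population of n = 120" (section 4). "The number was found to be 42 patients in each group, for a total n = 84" (section 7c). The MCID is 1.4 cm (section 7c); its use as the noninferiority margin is implied, not stated.

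**Inputs not in the documents.** The SD of VAS, the alpha, the power, and the share of VAS variance due to site (ρ).

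**1. The plan's own figure.** The 42 per group cannot be reproduced, because SD, alpha and power are missing. With true difference 0, n = 2·SD²·(z₁₋α + z_power)² / 1.4². Solving for n = 42 gives SD = 1.4·√21 / (z₁₋α + z_power):

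- one-sided 0.025, 80% power: 6.416 / 2.802 = 2.29 cm
- one-sided 0.025, 90% power: 1.98 cm
- one-sided 0.05, 80% power: 2.58 cm
- one-sided 0.05, 90% power: 2.19 cm

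I use 2.29 cm as a working assumption. The percentage changes in step 4 do not depend on it.

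**2. Chance imbalance under one list.** With 60:60 overall and 30 per site, the number in one arm at a site is hypergeometric, with SD √(30 × 0.5 × 0.5 × 90/119) = 2.38. A given site splits 20:10 or worse with probability 5.7%. For at least one of the four sites the probability is about 19% (18.8% by exact enumeration). For 19:11 or worse it is about 40%.

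**3. How far this moves the estimate.** The site contribution to the arm difference has SD √(2·ρ·SD²/60). At SD 2.29 cm:

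- ρ = 0.05: 0.09 cm
- ρ = 0.10: 0.13 cm
- ρ = 0.20: 0.19 cm

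This movement is centred on zero and is already inside the unadjusted standard error. In simulation (5,000 trials per scenario, ρ from 0 to 0.20), the mean error was −0.01 to 0.00 cm. Two-sided type I error was 4.9–5.6% for the t-test and 4.8–5.6% for the rank-sum test, nominal within simulation error.

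**4. Precision.** The variance of the difference is 2·SD²/n unadjusted, and 2·SD²·(1−ρ)/n with site stratified and adjusted. The interval therefore shrinks by 1 − √(1−ρ). The unadjusted 95% half-width at 60 per arm is 1.96 × 2.29 × √(2/60) = 0.82 cm.

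| ρ (assumed) | Adjusted half-width, 60 per arm | Shorter by | Power at 42 per arm (80% unadjusted) |
|---|---|---|---|
| 0.05 | 0.80 cm | 2.5% | 82% |
| 0.10 | 0.78 cm | 5.1% | 84% |
| 0.20 | 0.73 cm | 10.6% | 88% |

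Under a single list with 60 per arm, simulated noninferiority power was 91% unadjusted, against 92%, 93% and 95% adjusted.

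**5. If lists are held by site.** Balance within site is then close to automatic. The unadjusted standard error still includes site variance that the allocation has removed, so the actual two-sided type I error is P(|Z| > 1.96/√(1−ρ)). At ρ = 0.10 this is P(|Z| > 2.07) = 3.9%, and at ρ = 0.20 it is P(|Z| > 2.19) = 2.8%. Simulation of the t and rank-sum tests agreed: about 4% and about 3%.

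**The case against.** The strongest reply is that randomisation already does the work. Chance imbalance is ordinary sampling error, the unadjusted standard error covers it, and the precision at stake is small. The plan also has slack. The enrolment text reads "The sample size will enroll 120 (to account for 15% drop out rate) patients total", which leaves 120 × 0.85 = 102 evaluable patients against the 84 required. All of this stands, and it limits the point to efficiency and robustness.

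Some stronger readings are tempting, but the documents do not support them.

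- **Confounding.** A reader might infer that site confounds the comparison. Under random allocation it does not: step 3 finds no mean error and a nominal type I error.
- **Uneven training.** A reader might infer that injector training differs by site. Section 4 plans training for the surgeon at every site before enrolment, which is a standardising step. The operators differ; a difference in training is not shown.
- **Two separate harms.** The shift in the estimate and the inflation of the error variance are the same quantity. For example, site means at −1.5, −0.5, +0.5 and +1.5 cm (assumed) have variance 1.25, and √(2 × 1.25/60) = 0.204 cm is exactly that variance's part of the standard error. Such a spread is also at the high end: against a within-site SD of 2.3 cm it implies a site share of 1.25/(1.25 + 5.29) = 19%.
- **A site term settles the block-agent question.** It does not. A different agent or operator at one site would make the treatment effect itself differ, and neither balance nor a site main effect removes that. About 15 patients per arm per site cannot establish it either. Which agent a site uses is a clinical matter, and this point asks for no restriction on it.

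Two limits also stand. The 19% figure depends on a single list, which the documents do not confirm. Section 5 also lists three operative hospitals under one of the four sites, so a four-level site term would not fully capture differences in discharge practice.

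**Conclusion.** The point holds as a matter of precision and robustness, not validity. Site should be in both the allocation and the analyses, and gender, as the stratifier, should be in the analyses too. The gain is modest: a confidence interval about 3% to 11% shorter for an assumed site share of 5% to 20%. If the share is negligible, there is essentially no gain. The planned enrolment could absorb a loss of this size.

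The recommendation does not depend on how the lists are held. With one list, the present plan leaves a roughly 19% chance of at least one markedly unbalanced site and no means of correcting for it. With site-held lists, the unadjusted tests are conservative. The result rests on exact 1:1 allocation overall, equal site sizes and assumed values of ρ. The half-widths and powers also rest on the assumed SD of 2.29 cm.

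**What to change.** - State how the randomisation lists are held and generated. Randomise in permuted blocks within site, keeping gender as a second factor if wanted.
- Add site and gender as fixed effects to the mixed model.
- Replace the pooled rank-sum tests with a site-stratified version (van Elteren) at 24 hours and the other time points. Use a site-stratified test for day of discharge.
- Record the block agent actually given to each patient, and report the treatment effect by site descriptively, without a claim to test heterogeneity.

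The cost is a new allocation list and a few lines of SAP text. Site by gender makes up to 8 strata, with some incomplete blocks, and the site term uses three degrees of freedom. If site explains nothing and a single list was used, adjustment lengthens the interval by about 1% (simulated half-width 0.837 against 0.826 cm). If recruitment has already begun, the analysis changes can still be made before any unblinded look at outcomes.

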**2. Objectives (include all primary and secondary objectives)**

**Aim #1:** Determine clinical outcomes as they relate to pain control of the interscalene nerve block vs. liposomal bupivacaine injection in patients undergoing total shoulder arthroplasty.

This will be evaluated using the Visual Analog Scale (VAS) pain score and pain medication data and side effects from opioids (nausea/vomiting, GI distress, itching, etc) from inpatient medical records and through daily follow-up questionnaires after patients are discharged until 96 hours after surgery. Data will be collected at routine clinical follow up appointments after surgery.

**Aim #2:** Determine the length of stay of liposomal bupivacaine compared to interscalene nerve block in patients undergoing total shoulder arthroplasty and calculate costs associated with any differentials.

**3. Background** (briefly describe pre-clinical and clinical data, current experience with procedures, drug or device, and any other relevant information to justify the research)

We conducted a retrospective cohort analysis of 58 shoulder arthroplasties performed by a single surgeon. Patients who underwent total, reverse, and hemiarthroplasties were included. The control group included patients who received interscalene nerve blocks for postoperative pain control. The experimental group included patients who received periarticular liposomal bupivacaine injections. Baseline demographic data included age, sex, body mass index (BMI), and American Society of Anesthesiologists' (ASA) classification of physical health. We measured length of stay (LOS), pain medication administration, numeric rating scale (NRS) pain scores at four time intervals postoperatively (0.5 hours, 8-14 hours, 18-24 hours, 27-36 hours). Statistical analysis was performed.

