There were 21 patients in the IS nerve block group and 37 patients in the liposomal bupivacaine group who met all inclusion criteria. Baseline demographic data for age ( $p=0.53$ ), sex ( $p=0.71$ ), BMI ( $p=0.09$ ), and ASA ( $p=0.33$ ) did not differ between groups. The primary outcome measure, NRS pain score, showed no significant differences between groups at 0–1 hours after surgery ( $P = .99$ ) or 8–14 hours after surgery ( $P = .208$ ). At 18–24 hours after surgery, the liposomal bupivacaine group had a lower mean NRS score than the ISNB group ( $P = .001$ ). This was statistically significant when taking repeated measures of variance into account (Fig. 1). Mean NRS score was also lower for the liposomal bupivacaine group at 27–36 hours after surgery ( $P = .029$ ). This was not statistically significant when repeated measures of variance were considered (Table II).

There was no difference in the amount of intravenous acetaminophen given during the hospital stay between groups. There was no statistically significant difference in opioid consumption on postoperative day 1 in the hospital ( $P = .59$ ). However, there were significant differences between groups on postoperative days 2 and 3 (Fig. 2). On postoperative day 2, the ISNB group required significantly more opioids (112 mg) than the liposomal bupivacaine group (37 mg) ( $P = .001$ ). The ISNB group also required significantly more opioids (25 mg) on postoperative day 3 than the liposomal bupivacaine group (5 mg) ( $P = .002$ ).

Sixteen of 37 patients in the liposomal bupivacaine group and 2 of 21 in the ISNB group (Table III) were discharged on the day after surgery. The mean LOS was  $46 \pm 20$  hours for the liposomal bupivacaine group and  $57 \text{ hours} \pm 14$  hours for the ISNB group ( $P = .012$ ).

There were no major cardiac or respiratory events in either group. No long-term paresthesias or neuropathies were noted. There were no readmissions for either group.

Liposomal bupivacaine injections may provide better pain control 18-24 hours after surgery and shorten hospital stays after shoulder arthroplasty compared to interscalene nerve blocks as a means of postoperative pain control. Based on these results, larger analytic studies including randomized trials should be performed to explore the potential benefits of liposomal bupivacaine injections for pain control after shoulder arthroplasty.

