## 6. Drugs/ Substances/ Devices

- a. The rationale for choosing the drug and dose or for choosing the device to be used.

Drug and dosing used are the same as in the prior retrospective study.

- b. Justification and safety information if FDA approved drugs will be administered for non-FDA approved indications or if doses or routes of administration or participant populations are changed.

N/A

- c. Justification and safety information if non-FDA approved drugs without an IND will be administered.

N/A

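### The interscalene block anaesthetic is written as both 5% and 5 mg/1 mL, which differ tenfold, and no other section resolves the conflict

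*Combined protocol and SAP*

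**What the plan says.** Section 4a, item 3 (Surgery/Inpatient Stay) specifies the Group 1 treatment. Patients are to be "given a single shot block in the preoperative area by a fellowship-trained anesthesiologist", and the content of the injection follows: "The shot will contain a local anesthetic like 5% Ropivacaine (5 mg/1 mL". No volume and no total dose are given.

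Section 6a, on the choice of drug and dose, adds only this: "Drug and dosing used are the same as in the prior retrospective study". Section 3 (Background) reports that study and identifies its control arm in one sentence: "The control group included patients who received interscalene nerve blocks for postoperative pain control".

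The Group 2 entry in section 4a also contains a percentage strength, for a different drug: "local 0.5% bupivacaine-epinephrine will also be used not to exceed dose limits".

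**The concern.** A percentage followed by a bracketed mass per volume is normally one strength written two ways. Here the two forms do not describe the same solution, so a reader cannot tell from the text which strength is meant.

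The sentence carries weight because it is the only place in the available text that names ropivacaine or gives any strength for the block. The control arm is planned at 60 of the 120 patients, with enrolment at four sites. Section 4a provides for surgeons to be trained in the Exparel injection before enrolment and describes nothing equivalent for the block. For the block strength, this line is therefore the only written specification in the available text.

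Two things are at stake. Read literally, a tenfold conflict in the strength of an injected local anaesthetic is a potential hazard to patients. It also leaves the strength of the control treatment unclear in a trial whose sample size was set for a noninferiority comparison with that treatment.

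**Working it through.** **Inputs.** Both strengths come from the Group 1 entry in section 4a: "5% Ropivacaine (5 mg/1 mL". The document does not define the percentage. I take it as weight/volume, the ordinary convention for a drug solution and the one that matches the mass-per-volume form in the bracket.

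**Conversion.** A weight/volume percentage is grams per 100 mL, so mg/mL = % × 1000 / 100 = % × 10.

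| Form in the text | Conversion | Result |
|---|---|---|
| 5% | 5 g/100 mL = 5000 mg/100 mL | 50 mg/mL |
| 5 mg/1 mL | 500 mg/100 mL = 0.5 g/100 mL | 0.5% |

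The stated equivalence does not reproduce: 5% does not convert to 5 mg/mL, and 5 mg/mL does not convert to 5%.

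**Size.** Ratio: 50 / 5 = 10. Difference: 50 − 5 = 45 mg in each mL. For any volume V mL, the amounts are 50V mg and 5V mg, and the ratio remains 10. No volume has to be assumed.

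**Whether another part of the protocol settles it.**

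- Section 6a defers to the retrospective study and gives no figure.
- Section 3 describes that study's control arm only as interscalene nerve blocks. The mg amounts it reports are opioid consumption: "the ISNB group required significantly more opioids (112 mg) than the liposomal bupivacaine group (37 mg" on postoperative day 2, and 25 mg against 5 mg on day 3. None is a block dose.
- The 0.5% figure in section 4a is for bupivacaine-epinephrine in the other arm and says nothing about ropivacaine.
- With no block volume or total dose stated, the strength cannot be worked back from a total.

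No available section resolves the conflict. Front matter and any consent pages were not available and could not be checked.

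**The case against.** The arithmetic is not in dispute. The case for treating the point lightly has four parts.

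1. *The sentence is illustrative.* The word *like* makes ropivacaine an example, an anesthesiologist chooses and gives the block, and section 7d says that "both techniques are in routine use in our current clinical practice". Nothing shows that drug is drawn up from this line. This stands as a limit on the hazard: an actual tenfold error is unlikely, and none is shown. It does not reconcile two strengths given for the same named example, and it relies on the clinician overriding the text.

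2. *A decimal point may have been lost when the PDF was read.* This is possible and cannot be excluded. The other percentage in section 4a kept its decimal, but it has a leading zero and so is weak evidence about a bare point. The p-values in section 3 printed without a leading zero, such as P = .99 and P = .208, also kept theirs. Loss is therefore possible but unsupported. Confidence is high that the available text conflicts, and somewhat lower that the source PDF does. One look at the source settles it.

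3. *Reconciling the figures will not fully define the control treatment.* This stands. The agent is only an example and no volume is given, and both would remain so after the correction. The retrospective study also covered a single surgeon, whereas this trial has four sites.

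4. *The statistics are untouched.* This also stands: the planned sample size, the margin and the analysis do not depend on the block strength.

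**Conclusion.** The concern holds. The two strengths given for the control injection contradict each other by exactly a factor of 10 (50 mg/mL against 5 mg/mL), and no available section resolves the contradiction. The result rests on reading the percentage as weight/volume and on the text as extracted from the PDF.

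The point is a must-fix despite the mitigating facts. The error sits in the operative procedures section and concerns the strength of an injected drug in a trial arm. It has no internal cross-check and costs almost nothing to correct. The claim goes no further than a potential hazard and an ambiguous control strength.

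**What to change.** The sponsor should check the percentage and the mg/mL figure in section 4a against the source dosing that section 6a relies on, correct the line so that the two forms agree, and notify the four sites. If the source PDF turns out to be consistent, the point closes. Which figure is right is for the sponsor to establish, and no agent, strength or volume is proposed here.

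The cost is a one-line protocol correction, a look at the study team's own retrospective records and a notice to sites. No statistical section needs to change.
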